**Aim 3. Estimate regression-based norms and reliable change indices**

Title: Clinical Investigation Plan		Author: [name]		Company Restricted
DocID: ICBE-2-28674	Version: 2.0	Date: 2019-02-18	Status: Approved	Page: 26 of 35
IRBMANAGER PILOT – QI PROJECT				

The data collected can be used to establish regression-based norms. 250 (up to 300) participants (group A&C, phase 1 and group E) will be included in the norm group. These norms can be used for the IntelliSpace Cognition tool and may be updated at a later point in time.

Reference scores (for age, educational level, gender, and ethnicity) will be generated using linear regression techniques. We will additionally estimate regression based reliable change indices.

**Aim 4. Estimate factor loadings for cognitive model describing**

We have developed a model of cognitive functioning using the latent variable part of structural equation modelling (which is identical to the CFA described above). We will fit the ISC model of cognitive functioning on the digital test data from Group A, C, and E, yielding a sample of 250 (up to 300) participants for the CFA, further increasing the subject-to-variable ratio to ~12:1.

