### Primary objective:

The study has four aims.

1. To compare the psychometrics of digital and paper-pencil cognitive tests. Score distributions, test-retest reliability, and construct validity of the following tests will be compared: Trail Making Test (TMT), Rey Osterrieth Complex Figure Test (ROCFT), Digit Span Test, Controlled Oral Word Association Test (COWAT), Category Fluency Test, Rey Auditory Verbal Learning Test (RAVLT), Clock Drawing Test, Star Cancellation Test, O Cancellation Test, Mini Mental Status Exam 2 (MMSE-2).
2. To assess the degree of agreement between the algorithm and manual scores for the digital Rey Osterrieth Complex Figure Test and Clock Drawing Test.
3. To estimate regression-based norms and reliable change indices.
4. To estimate factor loadings for a structural equation model describing cognition in terms of distinct cognitive domains.

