### Primary hypotheses

The following primary hypotheses will be tested in the study:

Aim 1.

- A. Digital and paper-pencil normed test scores are comparable. We consider the two versions of a test comparable when the digital normed score is on average within .3 sd of the paper normed score and the two normed scores correlate at least .6.
- B. Test-retest reliability of the digital tests is comparable to test-retest reliability of the paper-pencil tests. We consider the reliability to be comparable when we observe no significant difference in a z-test between the digital and the paper-pencil test-retest correlations.

Title: Clinical Investigation Plan		Author: [name]		Company Restricted	
DocID: ICBE-2-28674	Version: 2.0	Date: 2019-02-18	Status: Approved	Page: 20 of 35	
IRBMANAGER PILOT – QI PROJECT					

C. Construct validity of the digital tests is comparable to the construct validity of the paper-pencil tests. We consider construct validity to be comparable when confirmatory factor analysis yields the same factor structure for digital and paper-pencil tests.

Aim 2.

D. The score(s) provided by the ROCFT and Clock Drawing Test scoring algorithms on ISC are correlated highly (> .8) to the score provided by manual scoring for the same drawings.

Aims 3 & 4 have no accompanying hypotheses.

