**Claims and intended performance**

The study aims to provide information that can be used to substantiate the claims listed in the table below from the regulatory plan of ISC, along with the study aim covering the claim.

Claim	Description	Covered by Study Aim
1.	A scientific model developed with KOLs that translates raw test scores to cognitive domains	4
2.	Automated scoring algorithms that give reproducible scores time after time	2
3.	Digital tests have similar psychometrics to paper test measures	1
4.	Longitudinal reporting of performance at the level of cognitive domains	3 & 4
5.	Usability by Design – high "easy to use" score for elderly users	Secondary objective
6.	Usability by Design - high user satisfaction when using digital platform	Secondary objective

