**Aim 1 comparison of psychometrics.**

Hypothesis A: Digital and paper-pencil test scores are comparable.

For each test, we will first compute age-only referenced scores for digital and paper-pencil version separately. Referenced scores are computed based on the regression based norms (procedure described below under aim 3) and are represented as z-scores indicating a participant's deviation from what would be expected based on the norm sample for a participant with identical demographic characteristics. We then compute the correlation between digital and paper-pencil referenced scores within participants in group A and B (which are the groups in which participants completed both digital and paper-pencil versions of the tests), which needs to be  $r > .6$  to be considered comparable. Our planned sample size allows us to detect a correlation of  $r > .2$  with 80% power. We also perform an equivalence test for each test, comparing the distribution of digital normed scores with paper-pencil normed scores, using a two-one-sided-t-test approach (TOST; Schuirmann, 1987), with equivalence bounds of  $\pm .3$  sd, which we have 99% power to detect. Our planned sample size would allow us to detect equivalence with bounds of at least  $\pm .21$  with 80% power.

Hypothesis B: Test-retest reliability is comparable.

Test-retest reliability will be tested by examining for each test the correlation between the digital tests in phase 1 and phase 2 (group C) and comparing this to the correlation between the paper-pencil tests in phase 1 and phase 2 (group D). High test-retest correlations are expected ( $r > 0.7$ ), except for the ROCFT copy condition, since the scores of this condition generally show a moderate ceiling effect. The planned sample size for group C and group D each yield 80% power to detect  $r > .37$ .

Hypothesis C: Construct validity is comparable.

Construct validity will be investigated by means of two confirmatory factor analyses (CFA), one for each group (digital vs. paper-pencil). We expect to see that the factor structure that fits the paper-pencil data (phase 1, group B & D) well, will also fit the digital data (phase 1, group A & C) well. Assuming that at most two variables per test are included in the CFA, the subject-to-variable ratio is near 10:1 for each CFA.

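### Aim 4 fits only the sponsor's own domain model, so a good fit would not show that the cognitive domains are separable

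*Combined protocol and SAP*

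**What the plan says.** Section 5 (Primary objective) gives the fourth aim as "To estimate factor loadings for a structural equation model describing cognition in terms of distinct cognitive domains". The list of primary hypotheses adds that "Aims 3 & 4 have no accompanying hypotheses".

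The analysis in section 7, Aim 4, is a single step: "We will fit the ISC model of cognitive functioning on the digital test data from Group A, C, and E". The expected number analysed is 250, or 300 if group E is extended. The only figure given in support is a subject-to-variable ratio, "further increasing the subject-to-variable ratio to ~12:1". No one-factor, higher-order or merged-domain model is named. There is no fit threshold and no limit on domain correlations. The Pass/fail criteria entry only refers back to the preceding text, which contains nothing for Aim 4.

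The table of claims in section 5 assigns claim 1, "A scientific model developed with KOLs that translates raw test scores to cognitive domains", to Aim 4. It assigns claim 4, on longitudinal reporting at domain level, to Aims 3 and 4. Sections 2.2 and 3 describe domain scores as a product output, reported beside overall performance, norm-referenced and followed over time.

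**The concern.** A model with several domains can fit well for two different reasons: the domains are separate, or they are all the same thing and the model has room to say so by estimating correlations near 1. Fitting one model does not tell these apart; a comparison with a simpler model does.

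Hypothesis C does not fill the gap. It asks whether the structure that fits the paper data also fits the digital data, and a single factor in both formats would satisfy it.

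What is at stake is the reading of the domain scores. If two domains correlate close to 1 in this population, separate scores for them add little to the overall score, and a clinician who reads them as different abilities is over-reading them.

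**Working it through.** **1. The plan's own figure.** Groups A, C and E give 100 + 50 + 100 = 250, or 300 if E reaches 150. With ten digital tests and at most two variables each (section 7, Hypothesis C: "Assuming that at most two variables per test are included in the CFA, the subject-to-variable ratio is near 10:1 for each CFA") there are at most 20 variables. 250/20 = 12.5, which agrees with the stated ratio of about 12:1; 300/20 = 15. The ratio bears on the stability of the estimates and says nothing about separability. I take 20 indicators as the working case. The near 10:1 stated for Hypothesis C would imply 150/10 = 15, so the plan does not fix the number exactly.

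**2. Nesting.** With m freely correlated domains there are m(m−1)/2 domain correlations. Setting all of them to 1 gives the one-factor model. The domain model therefore always fits at least as well by chi-square. For m = 5 the difference is 5×4/2 = 10 degrees of freedom (160 against 170 with 20 indicators).

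**3. What the planned fit would show if one factor were true.** Maximum-likelihood CFA, 100 simulated data sets per scenario. Assumptions not in the documents: normal data, equal loadings, five domains of four indicators (also four of five).

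| One-factor truth | Domain model, mean CFI / RMSEA | One-factor model, mean CFI / RMSEA | Domain model meets CFI ≥ .95 and RMSEA ≤ .06 |
|---|---|---|---|
| n=250, loadings .5 | .990 / .011 | .988 / .011 | 98% |
| n=250, loadings .6 | .993 / .012 | .993 / .012 | 100% |
| n=250, loadings .7 | .996 / .011 | .996 / .011 | 100% |
| n=300, loadings .6 | .995 / .010 | .995 / .009 | 100% |
| n=150, loadings .6 (size of each Hypothesis C analysis) | .985 / .019 | .984 / .019 | 95% |

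Four domains of five indicators (n=250, loadings .6) gave the same picture: CFI .993 and RMSEA .011 for both models.

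**4. Whether the output would give a sign.** In these one-factor runs the estimated domain correlations averaged about 1, and the factor correlation matrix was not positive definite in 99% to 100% of runs. That sign is not specific: at n=250 and loadings .6 an improper matrix also occurred in 83% of runs at a true correlation of .95 and in 41% at .90.

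**5. What the missing comparison could do.** Share of runs in which the nested test (alpha .05, 10 df) rejects one factor:

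| True domain correlation | n=250, loadings .6 | n=250, loadings .5 | n=300, loadings .6 |
|---|---|---|---|
| .95 | 32% | not run | not run |
| .90 | 80% | 35% | 91% |
| .85 | 99% | not run | not run |
| .80 | 100% | 98% | 100% |

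With 100 runs, the Monte Carlo standard error at 80% is √(.8×.2/100) = 4 percentage points. When one factor was true, the test rejected in 1% to 13% of runs across the scenarios, against a nominal 5%.

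**6. A cut-off on the confidence limit.** One could require the upper 95% limit of every domain correlation to lie below .90. For four domains of three indicators, loadings .65 and n=250, the standard error at a true correlation of .80 is .059, so the expected upper limit is .80 + 1.96×.059 = .916. A given domain would pass in about 11% of samples. In a simulation of the same layout (loadings .6 to .7), the nested test rejected one factor in 60 of 60 runs at .80 and in 40 of 60 at .90. The cut-off would usually merge domains that the test separates.

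**The case against.** The strongest reply is that Aim 4 is an estimation aim. It carries no hypothesis, the word distinct describes the model being parameterised, and claim 1 speaks only of translating scores into domains. That stands: no promised test has been omitted. The gap lies between an estimation exercise and the domain-level output and claims assigned to it.

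A second reply is that the specification is not given. That also stands. If the domains were fixed as uncorrelated, one-factor data would fit badly (CFI .47, RMSEA .14 at n=250, loadings .6). The nesting argument is therefore conditional on correlated domains or an equivalent general factor. Reporting both overall and domain performance points that way but does not prove it. Even in the uncorrelated case the plan has no Aim 4 fit criterion to act on.

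Four stronger readings are tempting, and the documents do not support them:

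- A reader might infer that no planned result could reveal the problem. Step 4 shows that it could be visible; what is missing is a plan to look and to act.
- A reader might infer that the disclaimer in section 2.2, that the cognitive model has been scientifically validated for ages 55 to 80, rests on Aim 4. The documents do not tie it to any aim.
- A reader might infer that separability has never been examined. Section 3 reports a pilot with excellent fit in 148 healthy people and sensitivity to impairment in 51 stroke and 48 TBI patients. It does not say whether rival models were compared, so the statement can be made of this plan only.
- A reader might infer that differences between domain scores would be mostly noise. With an assumed reliability of .8, (.8 − .8φ)/(1 − .8φ) gives .44, .29 and .17 at correlations φ of .8, .9 and .95. But section 3 describes norm-referenced scores followed over time, not differences between domains.

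**Conclusion.** The concern holds in a limited form. Aim 4 fits the sponsor's model alone. If its domains may correlate, a good fit is expected whether or not the domains are separable, and Hypothesis C has the same limit. Within this plan, the separability of the domain scores behind claims 1 and 4 is not tested.

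The nesting is algebra. The sizes rest on assumed loadings, equal domain correlations, normal data and 20 indicators. On those assumptions the planned sample can separate domains from one factor at true correlations of about .85 or lower with loadings of .6, and about .80 with loadings of .5. It cannot do so reliably at .95. These figures are for the overall one-factor comparison; power for merging a single pair was not computed and will generally be lower.

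This should be corrected before the data are analysed. It does not affect enrolment or the estimation of the loadings themselves.

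**What to change.** In section 7, Aim 4, state the ISC model in full: the domains, their indicators, and whether the domains correlate. On the same data from groups A, C and E, also fit:

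- a prespecified one-factor model;
- models that merge the most highly correlated domain pairs, with the rule for choosing the pairs fixed before the data are seen.

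Report the nested chi-square tests, noting that a correlation of 1 is a boundary value so the usual reference distribution is approximate. Report the CFI and RMSEA differences, and every domain correlation with its 95% confidence interval. Say how an improper factor matrix will be handled. Describe domains as distinct only where the domain model fits better than these rivals.

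Do not adopt a rule that merges domains whenever the upper confidence limit reaches .90: at n=250 it would usually merge domains that truly correlate .80.

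The cost is a few extra model fits on data already being collected. The real downside is that the claim of distinctness may have to be limited for some domains.

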**Sample size**

The study will include a total of  $N = 400$  (up to  $N=450$ ) healthy individuals, without accounting for drop-out (see Figure 1 for the design); The tests will be scored by two well-trained raters. Moreover, to compute the inter-rater agreement between scoring algorithms and manual scoring we need six additional well-trained raters.

**Significance and power**

Please see above description.

**Expected drop-out rates**

The expected drop-out rate is 20%. The company that will recruit the participants will oversample by 20% to account for the drop-out rate, resulting in 80 additional participants recruited in addition to the 400 needed for the full design.

**Pass/fail criteria**

Please see above description.

**Interim analysis**

Not applicable.

**Termination of entire study on statistical grounds**

The study will be terminated if a sample size of  $N = 400$  with the specified distribution across age, gender, education level, and ethnicity cannot be achieved.

## 8 DATA MANAGEMENT

Data will either be captured on paper and later transcribed to the electronic case report forms (eCRFs) or directly reported into the eCRFs at the time of procedure completion. Digital test data will be captured with our digital software tools in the cloud. Ultimately, Philips will handle all data in the Datatrak system.

Researchers will be trained on the devices and the specific data management for the study prior to the start of the study. The researchers will be provided usernames and passwords unique to each researcher.

Paper source documentation (firstly documenting data on paper with later transcription into the eCRFs) shall be used for data metrics (e.g., informed consent, randomization, safety metrics captured elsewhere, eligibility metrics, standard Site forms, etc.).

Documents that may be used to capture source data on paper include, but are not limited to: standard Site forms, study diaries, or any of the Document Template forms, etc. Each paper form shall have adequate study/Site and subject identifiers and must be and remain legible. A blue or black pen should be used to document data. A pencil should never be used.

Title: Clinical Investigation Plan		Author: [name]		Company Restricted	
DocID: ICBE-2-28674	Version: 2.0	Date: 2019-02-18	Status: Approved	Page: 27 of 35	
IRBMANAGER PILOT – QI PROJECT					

Researchers will be provided with the required forms by Philips, a paper template of the fields required to complete the eCRF. These will allow researchers to identify which data points will require documentation across the study.

**Procedures**

1. The supplier will have a compliant procedure to assure the data collection is collected according the regulations and that the data is stored and cannot be altered.
  2. The data will be collected by Supplier and gathered by Philips after completion.
  3. Digital data will be stored in the (Philips) cloud which is HIPAA and part 11 compliant.
  4. Data will be reviewed and cleaned by Philips.
  5. Philips will handle all data in the Datatrak system.
- All systems that are being used are CFR part 11 compliant.

**Data retention**

Please see PIAsupport document for a detailed overview of data collected and their retention time. All records and documents pertaining to the study including, but not limited to, data and source documents, will be maintained by the sponsor for a period of 15 years. In order to avoid any possible errors, the researcher will contact the Sponsor prior to the destruction of any study records. The researchers will promptly notify the Sponsor in the event of accidental loss or destruction of any study records.

However the digital data generated by the study will be used as part of the ISC product as the ground norm data set of the device (see study objectives). These records will not be related to any patient ID, but will be delivered as part of the ISC product to future customers once the product is on the market.

**Quality Assurance**

The Sponsor or its designee will implement steps to maintain quality control (QC) and quality assurance (QA) to ensure that the study is conducted and data are generated, documented, and reported in compliance with the protocol, good clinical practice, and applicable regulatory requirements. This will be completed by Sponsor monitoring visits. Regular monitoring and an independent audit, if conducted, must be performed according to ICH-GCP. QC procedures will be implemented beginning the study data QC checks will be performed. Any missing data or data anomalies will be communicated to the researchers for clarification/resolution. It is the responsibility of the researcher to respond to all edits checks and queries. Stored data as well as all data modifications to stored data will be documented by the system and available in audit trails. Following written procedures, the monitors will verify that the clinical trial is conducted and data are generated, recorded, and reported in compliance with the protocol, GCP, and the applicable regulatory requirements. The researchers will provide direct access to all trial related sites, source data/documents, and reports for the purpose of monitoring and auditing by the sponsor, and inspection by local and regulatory authorities. In addition, post data submission, Philips (or contracted) Monitors, Project Statistician, and/or the Data Management group will remotely review data generated at different time points during the study. Data queries will be generated to resolve any discrepancies or concerns.

**9 AMENDMENTS**

Any changes to the clinical study protocol after initial ICBE approval are documented as protocol amendments. After ICBE approval, and prior to execution at the study site, the amendment will be:

- submitted and approved by the applicable IRB
- signed by the Investigator(s)

**10 DEVIATIONS**

Protocol deviations are any alteration or deviation from the ICBE-approved research plan as defined in the study protocol. This includes equipment failures during study procedures. The researcher will

Title: Clinical Investigation Plan		Author: [name]		Company Restricted
DocID: ICBE-2-28674	Version: 2.0	Date: 2019-02-18	Status: Approved	Page: 28 of 35
IRBMANAGER PILOT – QI PROJECT				

deviate from the protocol whenever necessary to protect the participant's health, rights or welfare and these types of deviations will be reported to ICBE and the external IRB as soon as possible. Major deviations must be reported to ICBE and the IRB as soon as possible. In non-urgent/emergent situations, the researcher will obtain ICBE-approval for the planned deviation in advance of performing the changed activity.

If the researcher anticipates that there will be future requests for the same deviation, then the protocol will be amended (and such amendments must be approved by ICBE and the IRB). A minor deviation is something that does not cause harm or have the potential to cause harm to the participant, and does not impact the integrity of the study. These shall be documented in the study file and uploaded to ICBE for their awareness. Other reasons for amendment requests include adding a study site, increasing the number of research participants, and extending the time to perform the study. If the study objectives and procedure or cohort changes or the study changes from non-medical to medical, this generates a new study (not an amendment).

**Corrective and preventive actions and principal disqualification criteria**

When necessary, there will be given additional training to the researchers to conduct the study according to protocol.

**11 DEVICE ACCOUNTABILITY**

The procedures for the accountability of investigational devices are in accordance with the Guidance. The access to investigational devices will be controlled and the investigational devices will only be used in the clinical investigation and according to the CIP.

The sponsor shall keep records to document the physical location of all investigational devices from shipment of investigational devices to the investigation sites until return or disposal. This record will be based on Validation ISC – device list.

The principal investigator or an authorized designee shall keep records documenting the receipt, use, return and disposal of the investigational devices. This is all documented in the Validation ISC – device list. This record shall include (if applicable):

- the date of receipt,
- identification of each investigational device (batch number/serial number or unique code),
- the expiry date, if applicable,
- the date or dates of use,
- subject identification,
- ate on which the investigational device was returned/explanted from subject, if applicable, and
- the date of return of unused, expired or malfunctioning investigational devices, if applicable.

